1 OBJECTIVE

The objective of this procedure manual is to provide the study site with clear and detailed information for the storage, handling, preparation and administration of clinical products used in the Bristol-Myers Squibb CA209-405.

The information within this procedure manual is intended to supplement Section 8 of the CA209-405 clinical protocol.

3.0 STUDY TREATMENT

Diluents for drug Dilution (Dextrose 5%, 0.9% NaCl), syringes, tubing for intravenous administration, and filters will be provided for by the clinical site by Bristol-Myers Squibb.

Refer to appropriate section of the clinical protocol (Study Drug) for dosing for Nivolumab and Ipilimumab.

3.1 NIVOLUMAB INJECTION

3.1.1 DESCRIPTION

Product Name	Nivolumab Injection (or BMS 936558), 100 mg/vial (10 mg/mL)
Product description and Packaging	Packaging: Vials assembled into white dispensing boxes containing 5 - 10 x 100 mg vials each. Vials: 10 cc Type I glass vial. 20 mm stopper and seal, respectively. Appearance: Clear to opalescent, colorless to pale yellow liquid, light (few) particulates may be present.
Product Ingredients	Each vial contains 100 mg Nivolumab

3.1.2 Handling and Dose preparation

As with all injectable drugs, care should be taken when handling and preparing Nivolumab. Whenever possible, Nivolumab infusions should be prepared in a laminar flow hood, glovebox, or safety cabinet using standard procedures for the safe handling of intravenous agents applying aseptic techniques. Gloves are required. If nivolumab solution comes in contact with the skin or mucosa, immediately and thoroughly wash with soap and water.

Dose Preparation and administration

Visually inspect drug product solution for particulate matter and discoloration prior to administration. Nivolumab is a clear to opalescent, colorless to pale yellow solution. Discard the vial if the solution is cloudy, discolored, or contains extraneous particulate matter other than a few translucent-to-white, proteinaceous particles. DO NOT SHAKE the vial.

Preparation

- Withdraw the required volume of Nivolumab and transfer into an intravenous container.
- Dilute Nivolumab with either 0.9% Sodium Chloride Injection, USP or 5% Dextrose Injection, USP to prepare an infusion with a final concentration ranging from 1 mg/mL to 10 mg/mL (see example below)
- Mix diluted solution by gentle inversion. Do not shake.
- Discard partially used vials or empty vials of Nivolumab.

Storage of Infusion

The product does not contain a preservative. After preparation, store the Nivolumab infusion either:

- at room temperature for no more than 4 hours from the time of preparation. This includes room temperature storage of the infusion in the IV container and time for administration of the infusion

or

- under refrigeration at 2°C to 8°C (36°F to 46°F) for no more than 24 hours from the time of infusion preparation.

Do not freeze.

Administration

Administer the infusion over 30 (+/- 6 minutes) minutes through an intravenous line containing a sterile, non-pyrogenic, low protein binding in-line filter (pore size of 0.2 micrometer to 1.2 micrometer). Do not coadminister other drugs through the same intravenous line. **Flush the intravenous line at end of infusion with appropriate amount of diluent (e.g. 15-20 ml) to ensure that the total dose is administered. Total infusion and flush time should equal to 30 (+/-) 6 minutes.**

Dose selection for Nivolumab should be assigned per subject as outlined in the study drug dosing section of the clinical protocol. When Nivolumab is administered in combination with Ipilimumab, the Nivolumab will be infused first, followed by the ipilimumab to start approximately 30 minutes after the Nivolumab infusion completion.

Preparation examples are listed below assuming at 77.2 kg patient weight.

Example 1: 1 mg/kg dose (rounding to nearest mg dose)

Nivolumab 77 mg (7.7 ml Nivolumab 10mg/ml solution, local rounding rules applicable) may be mixed with 52.3 ml NS or D5W to a total volume = 60 ml (concentration = 1.3 mg/ml) which can be infused over 30 minutes (+/- 6 min) at 1ml/min followed by flush

Example 2: 3 mg/kg dose (rounding to the nearest mg dose)

Nivolumab 232 mg (23.2 ml Nivolumab 10mg/ml solution, local rounding rules applicable) may be mixed with 36.8 ml NS or D5W to a total volume = 60 ml (concentration = 3.9 mg/ml) which can be infused over 30 minutes (+/- 6 min) at 1 ml/min followed by flush.

3.1.3 Product Storage and Stability

Nivolumab 100 mg vials for injection should be refrigerated at 2°C to 8°C (36°F to 46°F). Protected from light and **should not be frozen**. Do not use beyond the expiration date on the vial. Protect the vials from light by storing in the original package until time of use. Vials do not contain preservative and thus are intended for single use only and should be discarded after use and product reconciliation.

Nivolumab should not be infused concomitantly in the same intravenous line with other agents. No physical or biochemical compatibility studies have been conducted to evaluate the co-administration of Nivolumab with other agents.

3.2 Ipilimumab Injection

3.2.1 Description

Product Name	Ipilimumab Injection, 200 mg/vial (5 mg/mL), 40 ml.
Product description and Packaging	Packaging: Vials assembled into cartons containing 4 vial(s) each. Vials: 50 cc Type I glass vial. 20 mm stopper and seal. Appearance: Clear, colorless liquid. Light (few) particles may be present
Product Ingredients	Each vial contains 200 mg (40 ml) Ipilimumab for injection

3.2.2 Handling and Dose preparation

As with all injectable drugs, care should be taken when handling and preparing ipilimumab. Whenever possible, ipilimumab infusions should be prepared in a laminar flow hood, glovebox, or safety cabinet using standard procedures for the safe handling of intravenous agents applying aseptic techniques. Gloves are required. If ipilimumab solution comes in contact with the skin or mucosa, immediately and thoroughly wash with soap and water.

Dose Preparation and administration

Inspect parenteral drug products visually for particulate matter and discoloration prior to administration. Discard vial if solution is cloudy, there is pronounced discoloration (solution may have pale-yellow color), or there is foreign particulate matter other than translucent-to-white, amorphous particles. DO NOT SHAKE THE VIAL.

Preparation

- Allow the vials to stand at room temperature for approximately 5 minutes prior to preparation of infusion.
- Withdraw the required volume of ipilimumab and transfer into an intravenous bag.
- Dilute with 0.9% Sodium Chloride Injection, USP or 5% Dextrose Injection, USP to prepare a diluted solution with a final concentration ranging from **1 mg/mL to 2 mg/mL and stored in PVC, non-PVC or glass containers.** Mix diluted solution by gentle inversion. Discard partially used vials or empty vials of Ipilimumab as outlined in section 4.8 of the clinical protocol.

Administration

- Flush the intravenous line with 0.9% Sodium Chloride Injection, USP or 5% Dextrose Injection, USP after each dose.
- Administer diluted solution over 30 minutes through an intravenous line containing a sterile, non-pyrogenic, low-protein-binding in-line filter.

Ipilimumab should be dosed per patient or subject as outlined in the clinical protocol, study drug dosing section or as otherwise indicted by the principle investigator. When Ipilimumab is administered in combination with Nivolumab, the Nivolumab will be infused first, followed by the ipilimumab to start approximately 30 minutes after the Nivolumab infusion completion.

Example

For ease of practical administration a total volume of 150 ml has been selected. Other infusion volumes may be used however it is recommended to keep concentration range of 1 - 2 mg/ml.

3 mg/kg in a 77 kg patient

Ipilimumab 231 mg (46.2 ml ipilimumab 5mg/ml solution) may be mixed with 103.8 ml (local rounding rules exception) NS or D5W to a total volume of 150 ml which can be infused over 90 minutes at 1.7 ml/min (concentration = 1.5 mg/ml).

3.2.3 Product Storage and Stability

Ipilimumab 200 mg vials for injection should be refrigerated at 2°C to 8°C (36°F to 46°F). Protected from light and **should not be frozen**. Do not use beyond the expiration date on the vial. Protect the vials from light by storing in the original package until time of use. Vials do not contain preservative and thus are intended for single use only and should be discarded as outlined in section 4.8 of the clinical protocol.

Store the diluted solution for no more than 24 hours under refrigeration (2°C to 8°C, 36°F to 46°F) or at room temperature (20°C to 25°C, 68°F to 77°F) including preparation time, transit time and administration time.

Ipilimumab should not be infused concomitantly in the same intravenous line with other agents. No physical or biochemical compatibility studies have been conducted to evaluate the co-administration of ipilimumab with other agents.

4 SITE TEMPERATURE EXCURSIONS AND TRANSIT

Drug must be stored under the proper conditions as listed on the clinical supply label and outlined in the respective drug supply sections of the clinical protocol. If any temperature excursions are encountered during on site storage, please report these to BMS for assessment as outlined in the Bristol-Myers Squibb, "Investigational Medicinal Product (IMP) handling at Investigational Sites: Shipment, Receipt, Storage, Use Date Extension and Return/Destruction" guideline using the Temperature Excursion Response Form. See Appendix 1

Proper storage conditions must be maintained during movement of inventory within an investigational site. Storage conditions for medications requiring storage at 2°C to 8°C (36°F-46°F) must be maintained throughout the transport with documentation maintained within the site files. Where controlled storage conditions (for example, temperature, relative humidity, light, etc.) are required during transit, the necessary environmental controls must be in place to ensure that the drug product remains within the acceptable temperature range. Temperature monitoring devices such as min max device must be implemented during transit.

5 PRODUCT RECEIPT, ACCOUNTABILITY, AND DESTRUCTION

Drug Receipt

Shipment Inspection Instructions

1. Open box **immediately** upon receipt.
2. Carefully inspect kits ensuring all of the supplies were received in good condition, correct quantity received, and all of the container ID #'s were received as noted on packing slip.
3. Sign and date (date of receipt) packing slip and file with study-specific documents.
4. Log in all supplies in each shipment on the appropriate Clinical Supplies Inventory Form (provided separately)

Accountability

As per the clinical protocol it is the responsibility of the investigator to ensure that a current disposition record of investigational product accountability and reconciliation is maintained at each study site where study drug is inventoried and dispensed.

In addition, records or logs must comply with applicable country/local regulations and guidelines and should include:

- Amount received and placed in storage area
- Amount currently in storage area

- Label ID number or batch number
- Amount dispensed to and returned by subject, including unique subject identifiers
- Amount transferred to another area/site for dispensing or storage
- Non-study disposition (e.g. lost, wasted)
- Amount destroyed at study site, if applicable
- Amount returned to the Sponsor, if applicable
- Dates and initials of person responsible for Investigational Product (IP)
- Dispensing/accountability, as per the Site Signature and Delegation Log.

Study Drug Destruction

Study drugs (those supplied by BMS or sourced by the site/investigator) can be destroyed on site if local policies allow to do so. It is the Investigator's responsibility to ensure that arrangements have been made for the disposal, procedures for proper disposal have been established according to applicable regulations, guidelines and institutional procedures, and appropriate records of the disposal have been documented.

All drug destruction whether performed on or off site should be documented according to local policies and procedures and should be documented accordingly.

6 IRT and DATA COLLECTION

Not applicable

APPENDIX 1
Bristol-Myers Squibb
Temperature Excursion Response Form for Investigational Medicinal Products

Section A. To be completed by the site at the time of Site Storage Temperature Excursion:

Protocol Number:	Site Number/Investigator Name/Country:	
Description of Drug Products involved in Excursion:		
Batch number (s) printed on label:	Container numbers:	
Description of Excursion (temperature highs/lows and duration):		
Below label storage lower limit°C	Duration:.....	Low extreme t°:°C
Above label storage upper limit °C	Duration:.....	High extreme t°:°C
Reason for excursion:		
Has the issue been resolved?		
Have these specific containers been involved in a previous excursion? NO  YES  If yes, please provide:		
Batch number (s):	Container numbers:	Temperature highs/lows and duration
When is the next planned patient visit when these supplies may be dispensed?		
Excursion information submitted by: _____ Date: _____ Print/Signature/Title of site staff		

Section B. Usage Decision to be made by Bristol-Myers Squibb:

Temperature excursion details for the products listed above have been evaluated. Usage decision is based on the temperature data that were made available by the investigational site.

Conclusion (and comments):

All products are suitable for continued use

All products are **NOT** suitable for further dispensation. Please remove supplies from available inventory and work with your Site Manager/Site Monitor to have supplies destroyed and IVRS updated if applicable.

Assessment completed by: _____ **Date** _____
Print/Signature/Title

APPENDIX 2

Templates as provided via separate attachment or below may serve as a sample for dosage calculations and may be printed out and used to document any calculations and infusion times as required by the clinical study team. Content in this attachment may be added or omitted.

Drug Dose and Volume Calculator for IV Infusion	
Drug Product :	
Protocol number	
Patient name or ID:	
Preparation date and time:	
Drug Strength (mg/mL)	
Subject body weight (kg)	
¹ Dose in mg	
Volume of Drug (mL)	
Total Volume of infusion (mL)	
Volume of Diluent (mL) NS or D5W	
Infusion duration (min)	
Infusion Rate (mL/min)	
Infusion hang time	
Infusion completion time	

Note: If required, flush line with separate volume of same diluent (15-20 ml) as outlined in the study pharmacy manual

¹Reference protocol appendix section 4 (Study Drug) for patient dose per tier or cohort

DANA-FARBER CANCER INSTITUTE
Nursing Protocol Education Sheet

Protocol Number:	16-136
Protocol Name:	A Phase II Trial of Ipilimumab and Nivolumab in Leptomeningeal Metastases
DFCI Site PI:	[name]

****** Remember to check the [ALERT PAGE](#)******

SPECIAL NURSING CONSIDERATIONS UNIQUE TO THIS PROTOCOL

Study Design	
 Ipilimumab is a fully human monoclonal immunoglobulin (Ig) specific for human cytotoxic T lymphocyte antigen 4, which is expressed on a subset of activated T cells (Section 2.2.1) Nivolumab is a fully human monoclonal antibody that targets the PD-1 CD279 cell surface membrane receptor (Section 2.2.2) A cycle is defined as six weeks, with the exception of the nivolumab maintenance monotherapy phase in melanoma and renal cell carcinoma a cycle when each cycle will be 8 weeks (Section 5.1)
Dose Calc.	
 Nivolumab will be dosed as mg /kg Ipilimumab will be dosed as mg /kg The dosing calculations should be based on the body weight. If the subject's weight on the day of dosing differs by > 5% from the weight used to calculate the dose, the dose must be recalculated (Section 5.3)
Study Drug Administration	
Agent Administration Guidelines are found in Section 5.3
 
 For treatment schedule by histology, see Section 5.1. When study drugs are to be administered on the same day, separate infusion bags and filters must be used for each infusion. Nivolumab will be administered first. Ipilimumab will be administered approximately 30 minutes after completion of Nivolumab. The Ipilimumab infusion will start no sooner than 30 minutes after completion of Nivolumab infusion. An infusion window of +/- 10 minutes is allowed for both Nivolumab and Ipilimumab The criteria to treat is outlined in Table 1, and in section 5.2. Nivolumab is to be administered as a 30 minute IV infusion. Ipilimumab is to be administered as a 30 minute IV infusion.
Dose Mods & Toxicity	
Criteria to Treat, Dose Modifications/Dosing Delays for Toxicity are outlined in Sections 5.2 and 6
 
 There will be no dose modifications permitted. Dose reductions or dose escalations are not permitted (Section 5.3 and 6) This protocol uses NCI CTCAE criteria, version 4.0
Con Meds	
Concomitant Therapy Guidelines are in Section 5.4
 
 Antiemetic premedications should not be routinely administered prior to dosing of drugs. See Section 6 for premedication recommendations following a nivolumab or ipilimumab related infusion reaction

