3. PARTICIPANT SELECTION

3.1 Eligibility Criteria

- 3.1.1 Participants must have histologically or cytologically confirmed disease from any solid tumor.
- 3.1.2 Age ≥ 18 years.
- 3.1.3 ECOG performance status ≤ 2 (Karnofsky $\geq 60\%$, see Appendix A)
- 3.1.4 Life expectancy of greater than 3 weeks
- 3.1.5 Participants must have normal organ and marrow function as defined in Table 1, all screening labs should be performed within 14 days of treatment initiation.

Table 1 Adequate Organ Function Laboratory Values

System	Laboratory Value
Hematological	
Absolute neutrophil count (ANC)	≥ 1500 /mcL

Platelets	$\geq 100,000 / \text{mcL}$
Hemoglobin	$\geq 9 \text{ g/dL}$ or $\geq 5.6 \text{ mmol/L}$ without transfusion or EPO dependency (within 7 days of assessment)
Renal	
Serum creatinine OR Measured or calculated ^a creatinine clearance (GFR can also be used in place of creatinine or CrCl)	
$\leq \text{ Serum creatinine} \leq 1.5 \times \text{ULN}$ or creatinine clearance (CrCl) $\geq 40 \text{ mL/min}$ (if using the Cockcroft-Gault formula below):
 
Female CrCl = $(140 - \text{age in years}) \times \text{weight in kg} \times 0.85$ $72 \times \text{serum creatinine in mg/dL}$
 
Male CrCl = $(140 - \text{age in years}) \times \text{weight in kg} \times 1.00$ $72 \times \text{serum creatinine in mg/dL}$

Hepatic	
Serum total bilirubin	$\leq 1.5 \times \text{ULN}$ OR
	Direct bilirubin $\leq \text{ULN}$ for subjects with total bilirubin levels $> 1.5 \text{ ULN}$
AST (SGOT) and ALT (SGPT)	$\leq 3 \text{ ULN}$ OR $\leq 5 \times \text{ULN}$ for subjects with liver metastases
Albumin	$\geq 2.5 \text{ mg/dL}$
Coagulation	
International Normalized Ratio (INR) or Prothrombin Time (PT)	$\leq 1.5 \times \text{ULN}$ unless subject is receiving anticoagulant therapy as long as PT or PTT is within therapeutic range of intended use of anticoagulants
Activated Partial Thromboplastin Time (aPTT)	$\leq 1.5 \times \text{ULN}$ unless subject is receiving anticoagulant therapy as long as PT or PTT is within therapeutic range of intended use of anticoagulants

^aCreatinine clearance should be calculated per institutional standard.

- 3.1.6 Women of childbearing potential (WOCBP) must use appropriate method(s) of contraception. WOCBP should use an adequate method to avoid pregnancy for 23 weeks (30 days plus the time required for nivolumab to undergo five half-lives) after the last dose of investigational drug.

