5.2 Pre-Treatment Criteria

5.2.1 Cycle 1, Day 1

A serum or urine pregnancy testing is required within 72 hrs of study enrollment. Cycle 1, Day 1 labs will be used to confirm eligibility.

System	Laboratory Value
Hematological	
Absolute neutrophil count (ANC)	$\geq 1500 / \text{mcL}$
Platelets	$\geq 100,000 / \text{mcL}$
Hemoglobin	$\geq 9 \text{ g/dL}$ or $\geq 5.6 \text{ mmol/L}$ without transfusion or EPO dependency (within 7 days of assessment)
Renal	
Serum creatinine OR Measured or calculated ^a creatinine clearance (GFR can also be used in place of creatinine or CrCl)	$\leq \text{ Serum creatinine} \leq 1.5 \times \text{ULN}$ or creatinine clearance (CrCl) $\geq 40 \text{ mL/min}$ (if using the Cockcroft-Gault formula below): $\text{Female CrCl} = \frac{(140 - \text{age in years}) \times \text{weight in kg} \times 0.85}{72 \times \text{serum creatinine in mg/dL}}$ $\text{Male CrCl} = \frac{(140 - \text{age in years}) \times \text{weight in kg} \times 1.00}{72 \times \text{serum creatinine in mg/dL}}$
Hepatic	
Serum total bilirubin	$\leq 1.5 \times \text{ULN}$ OR
	Direct bilirubin $\leq \text{ULN}$ for subjects with total bilirubin levels $> 1.5 \text{ ULN}$
AST (SGOT) and ALT (SGPT)	$\leq 3 \text{ ULN}$ OR $\leq 5 \times \text{ULN}$ for subjects with liver metastases
Albumin	$\geq 2.5 \text{ mg/dL}$
Coagulation	
International Normalized Ratio	$\leq 1.5 \times \text{ULN}$ unless subject is receiving anticoagulant therapy

(INR) or Prothrombin Time (PT)	as long as PT or PTT is within therapeutic range of intended use of anticoagulants $\leq 1.5 \times \text{ULN}$ unless subject is receiving anticoagulant therapy
Activated Partial Thromboplastin Time (aPTT)	as long as PT or PTT is within therapeutic range of intended use of anticoagulants
^a Creatinine clearance should be calculated per institutional standard.	

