5.2.2 Subsequent Cycles

Pregnancy Test: Every 6 weeks. After discontinuation from nivolumab these should be repeated at approximately 30 days and approximately 70 days.

Laboratory testing prior to each dose: Within 72 hrs prior to re-dosing to include CBC w/ differential, LFTs, BUN or serum urea level, creatinine, Ca, Mg, Na, K, Cl, LDH, Glucose, amylase, lipase, TSH (with reflexive Free T4 and Free T3)

System	Laboratory Value
Hematological	
Absolute neutrophil count (ANC)	$\geq 1500 / \text{mcL}$
Platelets	$\geq 100,000 / \text{mcL}$
Hemoglobin	$\geq 9 \text{ g/dL}$ or $\geq 5.6 \text{ mmol/L}$ without transfusion or EPO dependency (within 7 days of assessment)
Renal	
Serum creatinine OR Measured or calculated ^a creatinine clearance (GFR can also be used in place of creatinine or CrCl)	
$\leq \text{Serum creatinine} \leq 1.5 \times \text{ULN}$ or creatinine clearance (CrCl) $\geq 40 \text{ mL/min}$ (if using the Cockcroft-Gault formula below):
 
Female CrCl = $\frac{(140 - \text{age in years}) \times \text{weight in kg} \times 0.85}{72 \times \text{serum creatinine in mg/dL}}$
 
Male CrCl = $\frac{(140 - \text{age in years}) \times \text{weight in kg} \times 1.00}{72 \times \text{serum creatinine in mg/dL}}$

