B: For melanoma, small cell lung cancer, breast cancer, bladder cancer and other solid tumors (except NSCLC and head and neck cancers): Nivolumab 1mg/kg every 3 weeks for 4 doses during induction. For renal cell cancer: nivolumab 3mg/kg every 3 weeks x 4 doses during induction.

^aAll screening procedures to be performed within 14 days of start of study treatment, with the exception of CSF with positive cytology, which can be 6 weeks prior to initiation of study treatment. C1D1 and Day 1 of subsequent cycles: For C1D1 only, screening assessments may serve as day 1 assessments, except serum pregnancy (within 72 hours of drug) and except in the event that there are any indications that the participant's condition is deteriorating for which laboratory evaluations should be repeated within 48 hours prior to initiation. For all subsequent cycles, required assessments should be performed within 3 days of scheduled cycle day 1.

^bPhysical examination must include neurologic assessment.

^cSerum chemistries: Serum chemistry tests include albumin, amylase, lipase, BUN, creatinine, ALT, AST, LDH, serum alkaline phosphatase, direct and total bilirubin, glucose, total protein, sodium, potassium, chloride, HCO3, calcium, uric acid and TSH. A reflexive free T4 and free T3 will be performed reflexively for out of range TSH values. Patients should also be tested for Hepatitis B virus surface antigens (HBV sAg) and hepatitis C virus ribonucleic acid (HCV antibodies) at screening only.

^dEKG should be obtained at baseline for screening and then as clinically indicated

^eSerum pregnancy test (women of childbearing potential) is required within 72 hours of C1D1 dose. Pregnancy will be performed every 6 weeks while on treatment, and at 30 days and 70 days post last dose of Nivolumab

^fCerebrospinal fluid will be collected every 3 weeks during the induction phase and every 4 weeks during the maintenance phase to assess disease status (will be sent for cell count, protein, glucose, cytology) and 10cc will be saved for correlative studies as described in Section 9.0

^gTissue collected as part of clinical care (e.g. from prior biopsy, craniotomy) will be collected. See Section 9 for specimen collection

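### The albumin eligibility limit in Table 1 and section 5.2.1 is printed in mg/dL, 1,000-fold below the same number in g/dL, so as written it excludes no one

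*Combined protocol and SAP*

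**What the plan says.** Criterion 3.1.5 makes the organ-function limits in Table 1 a condition of entry and fixes the timing: "all screening labs should be performed within 14 days of treatment initiation". Section 5.2.1 reprints the table for the first dose and adds: "Cycle 1, Day 1 labs will be used to confirm eligibility". In both tables the hepatic block gives the albumin limit as at least 2.5 mg/dL, and the hematology block gives hemoglobin as at least 9 g/dL (or 5.6 mmol/L). Both tables also cap INR or PT, and aPTT, at 1.5 times ULN, with an exception for anticoagulated patients in therapeutic range.

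Section 4.1 has an investigator confirm eligibility and a study-team member complete a protocol-specific checklist.

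For the tests themselves, footnote c of the Study Calendar (section 10) reads: "Serum chemistry tests include albumin, amylase, lipase, BUN, creatinine, ALT, AST, LDH, serum alkaline phosphatase, direct and total bilirubin, glucose, total protein", and continues with electrolytes, uric acid and TSH. The pre-dose list in section 5.2.2 begins: "Within 72 hrs prior to re-dosing to include CBC w/ differential, LFTs, BUN or serum urea level, creatinine". Neither list names PT, INR or aPTT.

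The nursing sheet states, under study drug administration: "The criteria to treat is outlined in Table 1, and in section 5.2". Its next relevant row says that criteria to treat, dose modifications and delays "are outlined in Sections 5.2 and 6".

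**The concern.** An eligibility limit is meant to separate patients who may enter from those who may not. The printed albumin limit is so low that no real result falls below it. The criterion therefore does nothing if read literally. If staff silently read it as g/dL, they apply a rule that the protocol does not contain. In the first case a patient with very low albumin is formally eligible. In the second, a patient turned away for albumin of 2.0 g/dL was turned away against the written text. A checklist copied from Table 1 would carry the same fault.

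A smaller inconsistency sits in the same tables. The coagulation limits are binding at entry, but staff who order tests from the calendar would not draw them, which invites missing eligibility data.

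**Working it through.** **Albumin: inputs**
- Limit in Table 1 (section 3.1): 2.5 mg/dL.
- Limit in section 5.2.1: 2.5 mg/dL, the same number and unit.
- Unit of hemoglobin in both tables: g/dL.

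**Step 1, conversion.** 1 g = 1,000 mg, so 2.5 mg/dL ÷ 1,000 = 0.0025 g/dL. The same number in g/dL is 2.5 ÷ 0.0025 = 1,000 times higher.

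**Step 2, effect on individual results.**

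| Albumin (g/dL) | In mg/dL | Printed limit (≥ 2.5 mg/dL) | Limit at 2.5 g/dL |
|---|---|---|---|
| 1.0 | 1,000 | passes | fails |
| 1.5 | 1,500 | passes | fails |
| 2.0 | 2,000 | passes | fails |
| 2.4 | 2,400 | passes | fails |
| 3.5 | 3,500 | passes | passes |

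**Step 3, distance from plausible values.** The documents give no albumin distribution. Assume that patients lie between 1 and 5 g/dL. Then 1,000 ÷ 2.5 = 400 and 5,000 ÷ 2.5 = 2,000: every patient is 400 to 2,000 times above the printed limit, and the number excluded is 0.

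**Step 4, is albumin measured?** Yes. Footnote c lists it, and serum chemistry is marked in the Pre-Study column. Only the threshold is wrong, not the data collection.

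**Coagulation tests: comparison of sections**

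| Place | PT/INR and aPTT |
|---|---|
| Table 1 (3.1.5) | limits set |
| Section 5.2.1, Cycle 1 Day 1 | limits set |
| Induction, maintenance, and NSCLC/head-and-neck calendars: rows | not listed |
| Serum chemistry footnote c, all three calendars | not listed |
| Section 10, repeat labs after recent chemotherapy or targeted therapy | not listed (CBC and serum chemistry only) |
| Section 5.2.2 pre-dose list | not listed |

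The requirement at entry is therefore clear from 3.1.5 and 5.2.1. What is missing is its place in the schedule.

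**Operating characteristics.** The two-stage design in section 13.2 rests on survival rates of 18% and 43%, stages of 9 and 9 patients, and the cut-offs of 2 and 6 survivors. The albumin and coagulation limits enter none of these.

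**The case against.** The strongest reply is that the albumin unit is an obvious slip. A clinician would read g/dL, as for hemoglobin a few rows above, and nobody would apply the limit literally. Other criteria also set a floor on patient condition: ECOG status of 2 or better, life expectancy above 3 weeks, and the remaining organ-function limits. This is a fair argument about likely harm. It does not rescue the text: the unit is the same in two binding tables, and eligibility is confirmed against the written criteria.

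Three stronger readings are tempting, and the documents do not support them.

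- A reader might infer that the coagulation limits cannot work. They can: the limits are clear, and 3.1.5 with 5.2.1 already requires the results at entry. Only the schedule entry is missing.
- A reader might infer from the nursing sheet that Table 1, including coagulation, must be met before every dose. The sentence also cites section 5.2, which separates Cycle 1 Day 1 from later cycles, and the later row of the sheet points to sections 5.2 and 6 without naming Table 1. No protocol section applies INR or aPTT limits to re-dosing. The 5.2.2 table ends after the renal rows in the text available and may have been cut in reading the PDF, so nothing firm can be built on what it omits. The nursing sheet contains neither fault.
- A reader might infer that the coagulation limits are there to protect patients during CSF sampling. No section says so. Section 2.4 mentions both Ommaya/VP shunts and lumbar puncture as standard of care, and section 11.4 describes CSF as collected in clinical care.

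**Conclusion.** The albumin point stands. The limit is printed 1,000-fold below the same number in g/dL in both tables and, as written, excludes no one. The conversion needs no assumption. That the exclusion count is exactly zero rests on patients' albumin lying well above 0.0025 g/dL, which holds across the assumed 1 to 5 g/dL. That g/dL was intended is an inference from the hemoglobin unit and the size of the number, so the sponsor should confirm it.

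The coagulation point stands only as a minor inconsistency: tests required at entry appear in no calendar row or lab list.

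A reader might go further and infer that the 3-month survival result is compromised. The documents do not support that. They give neither the share of patients with low albumin nor survival by albumin level, and do not show that sites applied the limit literally. This is a correction to eligibility wording, with no effect on sample size, type I error or power.

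**What to change.** 1. In Table 1 (criterion 3.1.5) and section 5.2.1, change the albumin unit to g/dL, so that the limit reads at least 2.5 g/dL, with the sponsor confirming the number. Make the same change in any eligibility checklist derived from these tables.
2. As a minor consistency fix, add a PT/INR and aPTT row, marked in the Pre-Study column, to the two calendars that have that column (induction, and NSCLC/head and neck). The maintenance calendar needs no change.

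The cost is one unit edit in each of two tables and in any checklist, plus one row in each of two calendars. Albumin is already drawn at Pre-Study. The coagulation tests are already required at entry, so the new row formalizes an existing requirement; at most it adds one tube to a blood draw already scheduled. The nursing sheet needs no change for this point.
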